- **Safety follow-up visit:** will be performed approximately 90 days after the last dose of IMP. If any ongoing related AE/SAE is resolved or stabilized, no further follow-up visit is needed.

The expected duration of study intervention for participants may vary, based on progression date; median expected duration of study per participant is estimated as 11 months (up to 1 month for screening, a median of 6 months for treatment, and a median of 4 months for end-of-treatment assessments and safety follow-up visit).

Study interventions

Study interventions include tusamitamab ravidansine, ramucirumab, and pembrolizumab. To prevent hypersensitivity reactions, each administration will be preceded by premedication. Each cycle of treatment will have a duration of 2 weeks in the doublet cohort, and 3 weeks in the triplet cohort.

Investigational medicinal products

Ramucirumab

Ramucirumab will be administered prior to administration of tusamitamab ravidansine.

- **Formulation:** CYRAMZA® (ramucirumab) is a concentrate for solution for infusion supplied in 10 mL or 50 mL single-use vial. Each vial contains either 100 mg ramucirumab in 10 mL (10 mg/mL) or 500 mg ramucirumab in 50 mL (10 mg/mL).
- **Route of administration:** intravenous (IV) infusion.
- **Dose regimen:**
 - In the doublet cohort, ramucirumab will be administered as an 8 mg/kg IV infusion over 1 hour on Day 1 of every 2-week cycle. Each administration will be preceded by premedication (as per the approved product label) to prevent hypersensitivity reaction.

- In the triplet cohort, ramucirumab will be administered as a 10 mg/kg IV infusion over 1 hour on Day 1 of every 3-week cycle. Each administration will be preceded by premedication (as per the approved product label) to prevent hypersensitivity reaction.

Tusamitamab ravtansine

tusamitamab ravtansine infusion will start \geq 1 hour after the end of ramucirumab infusion.

- Formulation:
Tusamitamab ravtansine is supplied as a 25 mL extractable volume of concentrate for solution for infusion of 125 mg contained in a 30 mL type I glass vial.
- Route of administration: IV infusion.
- Dose regimen:
 - In the doublet cohort, tusamitamab ravtansine 100 mg/m² (or 80 mg/m², if deemed the appropriate dose by the SC) will be administered via IV infusion over 1 hour, 30 minutes on Day 1, and then every 2 weeks.

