6.6.4 Dose adjustment/dose delay

Dose adjustment and/or cycle delay are permitted in case of adverse reaction. In case of toxicity, cycle delays and dose modifications should be implemented according to Appendix 4 ([Section 10.4](#)). Every effort will be made to administer the full dose regimen and maximize dose intensity.

Dose adjustments will be made according to the worst grade of adverse reaction observed within a cycle. If a participant experiences several adverse reactions and there are conflicting recommendations, the most conservative dose adjustment recommended should be followed.

Administration of the study treatment will be discontinued in the event of a TEAE that persists despite appropriate dose modifications or any other AE that, in the opinion of the Investigator, warrants discontinuation.

Pembrolizumab, ramucirumab or tusamitamab rvtansine can be discontinued prematurely. The patient will remain on study treatment until the last IMP can be discontinued until disease progression, unacceptable AE, or the participant's or investigator's decision to stop the treatment. The reason for premature discontinuation will be captured in the appropriate eCRF page.

Dose modifications different from those stated in the protocol should be made only in consultation with the Sponsor unless required for immediate participant safety.

All changes to study treatment administration must be recorded in the eCRF.

In the event of neutropenia, therapeutic G-CSF should be administered according to the current American Society of Clinical Oncology (ASCO) guidelines ([23](#)). In case of neutropenia or febrile neutropenia, prophylactic G-CSF should be started and in case of second episode beside prophylactic G-CSF, then dose should be reduced.

The acceptable treatment window for tusamitamab rvtansine and ramucirumab and pembrolizumab administration is ± 2 days for a Q2W (doublet cohort) and ± 3 days for a Q3W administration (triplet cohort).

See Appendix 4 in [Section 10.4](#) for further guidance in dose modification or discontinuation. Approved product label should be followed for patient receiving ramucirumab treatment for supportive care and dose modification requirement due to not listed adverse events. During the conduct of the study, second dose reduction may be needed, and need to be decided case by case discussion with the sponsor.

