In case a dose reduction is necessary, the study intervention will be administered as shown in [Table 11](#) and [Table 12](#):

Table 11 - Dose modification for toxicity in doublet cohort

Drug name	Starting dose	1 st dose reduction	2 nd dose reduction
tusamitamab rvtansine	100 mg/m ² Q2W	80 mg/m ² Q2W	(not permitted)
ramucirumab	8 mg/kg Q2W	6 mg/kg Q2W	5 mg/kg Q2W

Table 12 - Dose modification for toxicity in triplet cohort

Drug name	Starting dose	1st dose reduction	2nd dose reduction
tusamitamab rfvansine	150 mg/m ² Q3W	120 mg/m ² Q3W	(not permitted)
ramucirumab	10 mg/kg Q3W	8 mg/kg Q3W	6 mg/kg Q3W
pembrolizumab	200 mg Q3W	(not permitted)	(not permitted)

Any patient who requires a tusamitamab rfvansine or ramucirumab dose reduction will continue to receive a reduced dose until discontinuation from tusamitamab rfvansine/ramucirumab/pembrolizumab or discontinuation from the study.

Any patient who has had 1 tusamitamab rfvansine dose reduction or 2 ramucirumab dose reductions and who experiences an event that would cause an additional dose reduction must be discontinued from tusamitamab rfvansine/ramucirumab.

If 1 of the 3 drugs (tusamitamab rfvansine or ramucirumab or pembrolizumab) is prematurely permanently discontinued, the other drug(s) can be continued until disease progression.

Retreatment of a patient requiring a dose delay of more than 1 month will need to be justified by an individual case risk-benefit assessment.

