8.2.6.5 Liver function tests

Hepatic enzyme increase has been reported with tusamitamab ravtansine administration as monotherapy or ramucirumab. Patients should be carefully followed and in case of Grade ≥ 3 abnormal liver function tests, additional liver function tests will be done every 2 to 3 days until recovery to baseline value. Tusamitamab ravtansine should be permanently discontinued in case of drug-induced Grade 4 liver enzyme increase. For stopping rules for ramucirumab administration, the current product leaflet should be followed.

Grade ≥ 3 (ie, $> 5 \times$ ULN) increased liver enzyme events should be reported as AESIs.

8.2.6.6 *Hypertension*

An increased incidence of severe hypertension (CTCAE Grade 3) has been reported in patients receiving ramucirumab as compared with placebo. In most cases, hypertension was controlled using standard antihypertensive treatment. Preexisting hypertension should be controlled before starting ramucirumab treatment. Monitoring of blood pressure is required during ramucirumab therapy. Every attempt should be made to control blood pressure to systolic <140 mmHg and diastolic <90 mmHg prior to starting treatment with ramucirumab. Routine clinical and laboratory monitoring is required in patients who again develop hypertension or experience a deterioration in previous hypertension.

Withhold ramucirumab for severe hypertension until medically controlled. Permanently discontinue ramucirumab for medically significant hypertension that cannot be controlled with antihypertensive therapy or in patients with hypertensive crisis or hypertensive encephalopathy.

8.2.6.7 *Proteinuria*

Proteinuria is an adverse effect for all therapies targeting the vascular endothelial growth factor (VEGF)/VEGFR-2 pathway, including ramucirumab. Proteinuria has been associated with ramucirumab in clinical studies; the majority of events were Grade 1 or 2.

Monitor proteinuria by urine dipstick and/or urinary protein creatinine ratio. If the result of the urine dipstick is 2+ or greater, perform a 24 hours urine collection for protein measurement.

Withhold ramucirumab for urine protein levels of 2 or more grams collected over 24 hours. Reinitiate ramucirumab at a reduced dose once the urine protein level returns to less than 2 grams over 24 hours. Permanently discontinue ramucirumab for urine protein levels greater than 3 grams over 24 hours, or in the setting of nephrotic syndrome.

8.2.6.8 *Bleeding/Hemorrhage*

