Event	Symptoms severity (Nadir) (NCI CTCAE v5)	Management of IMP dosing (ramucirumab)	Management of IMP dosing (tusamitamab rfvansine)	Supportive care guidelines
Febrile neutropenia	Grade 3 Absolute neutrophil count <1000/mm ³ with a single temperature of >38.3°C (101°F) or a sustained temperature of ≥38°C (100.4°F) for more than 1 hour	Delay cycle until absolute neutrophil count >1500/mm ³ . 1st episode administer next cycle at the same dose and administer G-CSF 2nd episode: administer ramucirumab at reduce dose 3rd episode: definitive discontinuation	Delay cycle until absolute neutrophil count >1500/mm ³ . 1st episode administer next cycle at the same dose and administer G-CSF 2nd episode: administer tusamitamab rfvansine at reduce dose 3rd episode: definitive discontinuation	To ensure relative dose intensity, G-CSF is recommended as secondary prophylaxis in all patients with Grade 3 febrile neutropenia ASCO guideline is recommended for supportive treatment if there are no defined clinical standards (23)
	Grade 4 Life-threatening consequences	Administration changes to be decided at the Investigator's discretion per product label	Administration changes to be decided at the Investigator's discretion. 1st episode: administer next cycle at reduced dose and administer G-CSF 2nd episode: definitive discontinuation	
Hypertension	Grade 3 Severe hypertension	Withhold ramucirumab until controlled with medical management, and restart at same dose	Administer tusamitamab rfvansine as planned	
	Grade 4 Severe hypertension that cannot be controlled with antihypertensive therapy	Definitively discontinue ramucirumab	Administer tusamitamab rfvansine as planned	
Proteinuria	First occurrence of increased urine protein levels greater than or equal to 2 g per 24 hours	Omit ramucirumab until urine protein level is ≤2 g per 24 hours; then resume ramucirumab at a reduced dose (in doublet cohort, 8 mg at 1st episode, then 5 mg if 2nd episode and in triplet cohort, 8 mg at 1 st episode, then 6 mg if 2d episode)	Administer tusamitamab rfvansine as planned	
	Reoccurrence of urine protein level greater than 2 g per 24 hours following initial dose reduction	Omit ramucirumab until protein level is ≤2 g per 24 hours; then resume ramucirumab at a reduced dose:(6 mg or 5 mg)	Administer tusamitamab rfvansine as planned	

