	Urine protein level greater than 3 g per 24 hours or in the setting of nephrotic syndrome	Definitively discontinue ramucirumab	Consider benefit/risk for the patient to continue or delay tusamitamab rfvansine infusion	

Event	Symptoms severity (Nadir) (NCI CTCAE v5)	Management of IMP dosing (ramucirumab))	Management of IMP dosing (tusamitamab rvtansine)	Supportive care guidelines
Hemorrhage	Grade 3 or 4	Definitively discontinue ramucirumab	Permanently discontinue tusamitamab rvtansine	
Gastrointestinal Perforation	All Grades	Permanently discontinue ramucirumab	Consider benefit/risk for the patient to continue or delay tusamitamab rvtansine infusion	
Arterial Thromboembolic Events	All Grades	Definitively discontinue ramucirumab	Administer tusamitamab rvtansine as planned	
Wound Healing Complications	All Grades	Definitively discontinue ramucirumab for wound healing complications requiring medical intervention	Consider benefit/risk for the patient to continue or delay tusamitamab rvtansine infusion	

a tusamitamab rvtansine is stable at least 7.5 hours in the infusion bag at room temperature. If necessary, a new infusion should be prepared with the remaining dose to be administered.

b The NCI CTCAE V5.0 grading is to be applied to keratopathy.

c Standard ocular examination per protocol includes visual acuity, slit lamp examination, Schirmer's test, and enquiring for ocular/visual symptoms.

d When possible at the site, photographs should be done when findings are first documented and to follow progression when relevant. Any additional relevant ocular examination can be done if indicated.

Abbreviations: ASCO = American Society of Clinical Oncology, ASOCT = Anterior segment optical coherence, BSA = Body surface area, ECG = Electrocardiogram, G-CSF = Granulocyte colony-stimulating factor, Hb = Hemoglobin, IMP = Investigational medicinal product, IV = Intravenous; LLN = Lower limit of normal, LVEF = Left ventricular ejection fraction, NCI CTCAE = National Cancer Institute Common Terminology Criteria for Adverse Events, RBC = Red blood cell.

Event	Symptoms severity (NCI CTCAE v5.0)	Management of IMP dosing (pembrolizumab)
Infusion-related reactions	Grades 1 or 2	Interrupt or slow the rate of infusion
	Grades 3 or 4	Permanently discontinue
Immune-mediated pneumonitis	Grade 2	Withhold
	Grades 3 or 4 or recurrent Grade 2	Permanently discontinue
Immune-mediated colitis	Grades 2 or 3	Withhold
	Grade 4 or recurrent Grade 3	Permanently discontinue

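### Appendix 4 gives the doublet cohort's reduced ramucirumab dose after a first proteinuria episode as 8 mg, the starting dose level; Table 11 sets 6 mg/kg

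*Protocol*

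**What the plan says.** The Protocol Synopsis fixes the doublet starting regimen: "ramucirumab will be administered as an 8 mg/kg IV infusion over 1 hour on Day 1 of every 2-week cycle". Table 11 in Section 6.6.4 then allows two reductions, to 6 mg/kg and to 5 mg/kg. For the triplet cohort, Table 12 starts at 10 mg/kg and allows 8 and then 6 mg/kg.

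Section 6.6.4 sends sites to two places for a toxicity. One sentence reads: "In case of toxicity, cycle delays and dose modifications should be implemented according to Appendix 4". The sentence that introduces the dose tables reads: "In case a dose reduction is necessary, the study intervention will be administered as shown in" Tables 11 and 12. The same section says that a participant who has had one tusamitamab ravtansine reduction or "2 ramucirumab dose reductions and who experiences an event that would cause an additional dose reduction must be discontinued" from those drugs.

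Section 8.2.6.7 withholds ramucirumab at 2 g/24 h or more and stops it for good above 3 g/24 h. Between those limits it says: "Reinitiate ramucirumab at a reduced dose once the urine protein level returns to less than 2 grams over 24 hours".

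Appendix 4 (Section 10.4) has three proteinuria rows:
- **First occurrence, 2 g/24 h or more:** "then resume ramucirumab at a reduced dose (in doublet cohort, 8 mg at 1st episode, then 5 mg if 2nd episode", followed by 8 mg and then 6 mg for the triplet cohort.
- **"Reoccurrence of urine protein level greater than 2 g per 24 hours following initial dose reduction":** resume at 6 mg or 5 mg, with no cohort named.
- **"Urine protein level greater than 3 g per 24 hours or in the setting of nephrotic syndrome":** ramucirumab is definitively discontinued.

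**The concern.** The first-occurrence row orders a reduced dose and then gives the doublet cohort the dose level at which it started. Appendix 4 is the event-by-event table a site would open when a urine protein result comes back high, so its figure is likely to be used.

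The matter at stake is dosing safety. A participant whose proteinuria reached 2 to 3 g/24 h on full-dose ramucirumab could be put back on full dose when the protocol means the dose to be lowered. Proteinuria is an acknowledged effect of this drug (Section 8.2.6.7), and urine protein of 3 g/24 h or more is a listed DLT (Table 5). There is a smaller consequence for the stopping rule in Section 6.6.4, which counts ramucirumab reductions: a resumption at 8 mg/kg is not one.

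**Working it through.** No power or sample-size calculation applies. The check sets the dose levels side by side and expresses each as a change from the starting dose.

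**Inputs.** Doublet start 8 mg/kg (Synopsis, Table 11); doublet reductions 6 and 5 mg/kg (Table 11; the same levels in SAP Table 7); triplet start 10 mg/kg, with reductions to 8 and 6 mg/kg (Table 12); Appendix 4 figures as printed, read as mg/kg.

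**Formula.** Reduction = (start − resumed dose) / start.

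| Cohort and step | Appendix 4 | Tables 11 and 12 | Reduction, Appendix 4 | Reduction, tables |
|---|---|---|---|---|
| Doublet, 1st episode | 8 | 6 | (8 − 8)/8 = 0% | (8 − 6)/8 = 25% |
| Doublet, 2nd episode | 5 | 5 | (8 − 5)/8 = 37.5% | 37.5% |
| Triplet, 1st episode | 8 | 8 | (10 − 8)/10 = 20% | 20% |
| Triplet, 2nd episode | 6 | 6 | (10 − 6)/10 = 40% | 40% |

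Three of the four steps agree; only the doublet first step does not.

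**Excess dose.** Relative to Table 11, the Appendix 4 figure gives (8 − 6)/6 = 33.3% more ramucirumab per infusion. The excess lasts until a second episode, when both sources arrive at 5 mg/kg.

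**Which figure is wrong.** Four features of the documents point to the Appendix 4 figure:
1. Its own sentence calls the dose reduced.
2. Section 8.2.6.7 requires a reduced dose after recovery.
3. The reoccurrence row presupposes that the first episode already lowered the dose.
4. SAP Table 7 places level −1 at 6 mg/kg (above 5.5 and up to 7) and treats anything above 7 mg/kg as the starting level.

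The two doses in the reoccurrence row fit the second reductions, 6 for the triplet and 5 for the doublet, although the cohorts are not named.

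**Window in which it applies.** Ramucirumab is withheld from 2 g/24 h and stopped above 3 g/24 h, so a resumption dose arises only for episodes of about 2 to 3 g/24 h.

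**Effect on the reduction count.** After two episodes the Appendix 4 path is 8, 8, 5, with one real reduction; the Table 11 path is 8, 6, 5, with two. Under SAP Table 7 a resumed 8 mg/kg stays in the starting interval and would not be counted as a reduction.

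**Units.** The proteinuria rows give doses in mg, whereas ramucirumab is dosed in mg/kg throughout. A total dose of 8 mg is implausible, so this is secondary, but it should be corrected in the same edit.

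**The case against.** The strongest reply is that the intention is plain and the harm unlikely. Both Appendix 4 and Section 8.2.6.7 call for a reduction, and Section 6.6.4 says that reductions are given as in Table 11. A reader who sees 8 mg must already correct the unit, which leads back to Table 11, where the answer is 6 mg/kg. On this view it is a typing slip that an alert investigator would catch.

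That lowers the probability of a dosing error but does not remove the error. Section 6.6.4 points to both sources and does not say which prevails when they differ. Its rule to take the most conservative adjustment is written for a participant with several adverse reactions, not for two tables that disagree about one event. A toxicity table should not depend on the reader noticing that its figure is wrong.

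Three further points limit the consequence:
- **Stopping rule.** Both paths reach 5 mg/kg at the second episode, and Table 11 has no lower level. The difference of one reduction against two is a difference in counting, and no different dose follows after the second episode. This point stands.
- **Exposure.** About 36 treated participants is only a ceiling. The first participant was enrolled on 28 October 2020, with about 12 months of enrolment and a median of 6 months of treatment planned. Wording that separates doublet from triplet belongs to the amendment of 20 December 2022. By plan, few doublet participants would still have been on ramucirumab by then. However, Section 7 lets those with clinical benefit continue after the cut-off, so the row can still apply. The row's wording before that amendment is not given.
- **One digit.** The finding turns on a single figure in one table cell. The other doses in these rows agree with the tables, and nothing suggests that this one was meant differently, but it is easily confirmed against the signed protocol.

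**Conclusion.** The concern holds. For the doublet cohort, the Appendix 4 first-episode dose is 0% below the start where Table 11 requires 25%; no text in either document reconciles the two. The error runs in the unsafe direction, by 33% per infusion, for participants who resume after a first episode of about 2 to 3 g/24 h. How many that is cannot be estimated from the documents.

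The conclusion rests on reading the printed mg figures as mg/kg. That 8 was written in place of 6, perhaps carried over from the triplet value in the same cell, is an inference; the conflict itself is not. The point concerns dosing safety only and leaves ORR, the sample size and the SAP rules as they are. It should be corrected because a safety instruction gives the wrong dose, not because many participants are likely to be affected.

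**What to change.** Rewrite the two resumption rows for proteinuria in Appendix 4 in mg/kg, matching Tables 11 and 12:
- **First-occurrence row:** doublet 6 mg/kg at the first episode, then 5 mg/kg at the second; triplet 8 mg/kg at the first, then 6 mg/kg at the second.
- **Reoccurrence row, labelled by cohort:** doublet 5 mg/kg; triplet 6 mg/kg.

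SAP Table 7 already follows Table 11 and needs no change. The cost is a clarification letter to sites or a short amendment, with no effect on design, sample size or analysis.

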10.5 APPENDIX 5: CONTRACEPTIVE GUIDANCE AND COLLECTION OF PREGNANCY INFORMATION

DEFINITIONS:

Woman of childbearing potential (WOCBP)

A woman is considered fertile following menarche and until becoming post-menopausal unless permanently sterile (see below).

If fertility is unclear (eg, amenorrhea in adolescents or athletes) and a menstrual cycle cannot be confirmed before first dose of study intervention, additional evaluation should be considered.

Women in the following categories are not considered WOCBP

1. Premenarchal
2. Premenopausal female with 1 of the following:
 - Documented hysterectomy
 - Documented bilateral salpingectomy
 - Documented bilateral oophorectomy

For individuals with permanent infertility due to an alternate medical cause other than the above, (eg, mullerian agenesis, androgen insensitivity), Investigator discretion should be applied to determining study entry.

Note: Documentation can come from the site personnel's: review of the participant's medical records, medical examination, or medical history interview.

3. Postmenopausal female
 - A postmenopausal state is defined as no menses for 12 months without an alternative medical cause.
 - A high follicle stimulating hormone (FSH) level in the postmenopausal range may be used to confirm a postmenopausal state in women not using hormonal contraception or hormonal replacement therapy (HRT). However, in the absence of 12 months of amenorrhea, confirmation with more than one FSH measurement is required.
 - Females on HRT and whose menopausal status is in doubt will be required to use one of the non-estrogen hormonal highly effective contraception methods if they wish to continue their HRT during the study. Otherwise, they must discontinue HRT to allow confirmation of postmenopausal status before study enrollment.

CONTRACEPTION GUIDANCE:

CONTRACEPTIVES^a ALLOWED DURING THE STUDY INCLUDE:

Highly Effective Methods^b That Have Low User Dependency *Failure rate of <1% per year when used consistently and correctly.*

- Implantable progestogen-only hormone contraception associated with inhibition of ovulation^b
- Intrauterine device (IUD)
- Intrauterine hormone-releasing system (IUS)^b
- Bilateral tubal occlusion
- Vasectomized partner

(Vasectomized partner is a highly effective contraceptive method provided that the partner is the sole sexual partner of the woman of childbearing potential and the absence of sperm has been confirmed. If not, an additional highly effective method of contraception should be used. Spermatogenesis cycle is approximately 90 days.)

Highly Effective Methods^b That Are User Dependent *Failure rate of <1% per year when used consistently and correctly.*

Combined (estrogen- and progestogen-containing) hormonal contraception associated with inhibition of ovulation^c

- oral
- intravaginal
- transdermal
- injectable

Progestogen-only hormone contraception associated with inhibition of ovulation^c

- oral
- injectable

Sexual abstinence

Sexual abstinence is considered a highly effective method only if defined as refraining from heterosexual intercourse during the entire period of risk associated with the study intervention. The reliability of sexual abstinence needs to be evaluated in relation to the duration of the study and the preferred and usual lifestyle of the participant.

ACCEPTABLE METHODS^d

- Progestogen-only oral hormonal contraception where inhibition of ovulation is not the primary mode of action
- Male or female condom with or without spermicide^e
- Cervical cap, diaphragm, or sponge with spermicide
- A combination of male condom with either cervical cap, diaphragm, or sponge with spermicide (double-barrier methods)^c

a Contraceptive use by men or women should be consistent with local regulations regarding the use of contraceptive methods for those participating in clinical studies.

b Failure rate of <1% per year when used consistently and correctly. Typical use failure rates differ from those when used consistently and correctly.

c If locally required, in accordance with Clinical Trial Facilitation Group (CTFG) guidelines, acceptable contraceptive methods are limited to those which inhibit ovulation as the primary mode of action.

d Considered effective, but not highly effective - failure rate of $\geq 1\%$ per year. Periodic abstinence (calendar, symptothermal, post-ovulation methods), withdrawal (coitus interruptus), spermicides only, and lactational amenorrhoea method (LAM) are not acceptable methods of contraception.

e Male condom and female condom should not be used together (due to risk of failure with friction).

COLLECTION OF PREGNANCY INFORMATION:

Male participants with partners who become pregnant

- The Investigator will attempt to collect pregnancy information on any male participant's female partner who becomes pregnant while the male participant is in this study. This applies only to male participants who receive study intervention.
- After obtaining the necessary signed informed consent from the pregnant female partner directly, the Investigator will record pregnancy information on the appropriate form and submit it to the Sponsor within 24 hours of learning of the partner's pregnancy. The female partner will also be followed to determine the outcome of the pregnancy. Information on the status of the mother and child will be forwarded to the Sponsor. Generally, the follow-up will be no longer than 6 to 8 weeks following the estimated delivery date but may last up to one year. Any termination of the pregnancy will be reported regardless of fetal status (presence or absence of anomalies) or indication for the procedure.

Female participants who become pregnant

- The Investigator will collect pregnancy information on any female participant who becomes pregnant while participating in this study. Information will be recorded on the appropriate form and submitted to the Sponsor within [24 hours] of learning of a participant's pregnancy. The participant will be followed to determine the outcome of the pregnancy. The Investigator will collect follow-up information on the participant and the neonate and the information will be forwarded to the Sponsor. Generally, follow-up will not be required for longer than 6 to 8 weeks beyond the estimated delivery date but may last up to one year. Any termination of pregnancy will be reported, regardless of fetal status (presence or absence of anomalies) or indication for the procedure.

- Any pregnancy complication or elective termination of a pregnancy will be reported as an AE or SAE. A spontaneous abortion (occurring at <22 weeks gestational age) or still birth (occurring at >22 weeks gestational age) is always considered to be an SAE and will be reported as such. Any post-study pregnancy related SAE considered reasonably related to the study intervention by the Investigator will be reported to the Sponsor as described in [Section 8.3.5](#). While the Investigator is not obligated to actively seek this information in former study participants, he or she may learn of an SAE through spontaneous reporting.
- Any female participant who becomes pregnant while participating in the study will discontinue study intervention.

